## 2. SYNOPSIS OF THE CLINICAL INVESTIGATION

TITLE	Clinical Outcome of Electrical Auricular Vagal Stimulation in Patients with Stable Symptomatic Chronic Heart Failure -a Pilot Study					
ACRONYM	(abbreviated title)					
NAME OF DEVICE	Dev1					
DESCRIPTION OF THE PROCEDURES	P-Stim® is an investigational device intended to deliver electrical auricular acupuncture in individuals suffering from heart failure. The device system is to be used only in accordance with the approved Investigational Plan on subjects who have signed an informed consent form. Device use is limited to the approved study investigators.					
OBJECTIVES	
In this study the effects of electrical auricular acupuncture on symptomatic chronic heart failure will be assessed.
 
Primary Objective:
 

- Six-minute walk test

 
Secondary Objective:
 

- Left ventricular ejection fraction (LVEF)

- New York Heart Association (NYHA) classification

- In addition the patient's quality of life (regarding to different areas in daily life, mobility etc.) will be assessed by a quality of life questionnaire (SF 36)

- Adverse events of acupuncture will be recorded

- Inflammatory cytokines TNF <math>\alpha</math>, IL6, NT-proBNP, CRP, will be collected to measure a possible influence of electrical auricular acupuncture on inflammation

- Ventricular and/or atrial arrhythmia documented in a subgroup of patients with implanted cardiac rhythm management devices.

					
TYPE OF THE INVESTIGATION	Prospective, single center, randomized, parallel group, double-blind, placebo-controlled					
PERIOD OF ENROLMENT	First patient First visit	1.1.20 13	Last patient First visit	31.12. 2013	Last patient Last visit	28.2.10 14
CENTER(S) / COUNTRY(IES)	1 center, Medical University Vienna, Austria					
PATIENTS / GROUPS	40 patients in 2 groups 20 patients per group Randomization ratio 1:1, stratification gender					
INCLUSION CRITERIA	

- Stable symptomatic chronic heart failure, defined by:

- NYHA Classification II-III

- Optimal medical treatment (ESC guidelines 2012) for at least 1 month

					

	
 
- LVEF <40%
 
- Patients must be able to understand study conditions
 
- No exclusion criteria
 
- Signed informed consent
 

EXCLUSION CRITERIA	
 
- Ventricular tachyarrhythmia within 1 month prior to base line visit
 
- Any electrical auricular vagal stimulation treatment within 6 months prior to base line visit
 
- Participation in another clinical trial within 3 months prior to base line visit
 
- Psoriasis vulgaris
 
- Hemophilia
 
- Cardiac pace makers
 

COMPARATIVE DEVICE	Placebo
CONCOMITANT MEDICATION/CON-COMITANT DEVICE	Not applicable
EFFICACY ENDPOINTS	Clinical outcome of heart failure definition see above
TOLERABILITY / SAFETY ENDPOINTS	Adverse Events will be recorded
QUALITY OF LIFE	SF 36 questionnaire
STATISTICAL METHODOLOGY	
 
• Primary Endpoint 6 minute walk test
 
• Null and alternative hypotheses: <math>H_0</math>: electrical auricular vagal stimulation does not increase 6min walk test <math>H_1</math>: electrical auricular vagal stimulation increases 6min walk test
 
• Type-I and -II errors - power. <math>\alpha</math> 0.05 (two sided) <math>\beta</math> 0.20 (Power =80%)
 
• Interim analysis
 
• Statistical methodology The primary end point (walking distance in 6 minutes) will be analysed by analysis of covariance, taking the baseline value as covariate into account, and the treatment group as factor.
 
• Continuous secondary outcome variables will be analysed by analysis of covariance as described above. Change in NYHA classification will be described by contingency tables, and the percentage of patients with an improvement in NYHA will be compared using a Fisher's exact test.
 
• Sample size calculation. We assume a clinically relevant difference in the improvement in walking distance of 30 meters comparing the electrically stimulated
 

	
acupuncture group to the Placebo group. Furthermore, we assume a standard deviation in the improvement of the walking distance of 30 meters (Kristen 2010). A sample size of 17 in each group will have 80% power to detect this clinically relevant difference between the groups using a two group t-test with a 0,050 two-sided significance level. Because of the possibility of drop-outs we include 2x20 patients.
 

• Main analysis set: Intention to treat

• Other endpoints

STUDY EXTENSION	.

## 4. INTRODUCTION

### 4.1 Background information

#### a) Nerve Supply of the auricle

Peuker et al found a heterogenous distribution of cranial branchial nerves and somatic cervical nerves in the auricle. The lateral surface of the auricle is innervated by the great auricular nerve (GAN), the auricular branch of vagus nerve (ABVN) and the auriculotemporal nerve (ATN). Peuker et al also provided an overview of the innervations pattern of the lateral surface of the auricle. ABVN mainly supplies the cymba conchae (100%), cavity of concha (45%), the tragus (45%) and the Antihelix (73%). Some parts of the lateral surface of the auricle show a double innervation.

#### b) Vagal stimulation in heart failure

Heart failure is characterized by an autonomic imbalance with withdrawal of vagal activity and increased sympathetic activity. This autonomic imbalance can be quantified by the BRS (Baroreflex sensitivity) or by heart rate variability. Lower BRS is related to a higher mortality in heart failure. During acute myocardial ischemia (when the heart dilates) vagal and sympathetic afferent fibers increase their firing. At the ventricular level, sympathetic fibers are dominant, which leads to a sympathetic excitation and to the cardio-cardiac sympathetic reflex.

This afferent sympathetic activity inhibits the cardiac vagal efferent activity.

#### c) The role of inflammatory cytokines in heart failure

Until a few years ago heart failure (HF) was considered a hemodynamic disorder. Recent studies however clearly show a correlation of HF to neurohormones. Several trials suggest an increased expression of TNF $\alpha$ , IL-6, IL-18, cardiotrophin-1 and Fas ligand as well as other chemokines in patients with HF. Some of these elevated neurohormones are also associated with a deterioration of LVEF (left ventricular ejection fraction) or NYHA Classification. Inflammation also plays a role in post-myocardial infarction remodelling. During the acute phase of myocardial infarction cytokines are an intrinsic response to the injury in the myocardium. The cytokines mainly involved in this process of wound repair, scar formation and compensatory hypertrophy are TNF $\alpha$ , IL-6 and IL-1 $\beta$ . While a moderate inflammatory response induces a survival activating factor enhancement pathway, a persistent inflammatory response may lead to heart failure.

For risk stratification and evaluation of therapeutic responses in heart failure, mainly NT-proBNP (natriuretic peptide) is used as biomarker. NT-proBNP also guides therapy in heart failure. In addition CRP (C-reactive protein) gained a leading role as an inflammatory biomarker in cardiovascular disease mainly because of its ability to reflect upstream inflammatory activity. A large clinical trial associated increased CRP levels with features of more severe HF and adverse clinical outcome.

Although NT-proBNP is a strong biomarker in HF, it is unlikely that it reflects all the pathogenic processes involved in this complex disorder. Therefore the role of other inflammatory cytokines in HF has to be investigated.

### 5.2. Rationale of the clinical investigation

Chronic heart failure is one of the most serious medical problems in industrial countries. Despite optimized heart failure therapy the prognosis remains bad. Raised inflammatory cytokines are causing skeletal muscle fatigue and activation of muscle ergoreceptors, subsequently leading to an

increase in ventilation, sensation of breathlessness, perception of fatigue and autonomic dysbalance. Novel approaches to heart failure therapy include selective electrical vagal stimulation to normalize autonomic balance. Vagal Stimulation however remains an invasive technique, which is restricted to therapy-resistant patients. Acupuncture has been shown to act pro-vagotonic and anti-inflammatory. In addition Kristen et al recently showed an improvement of exercise tolerance in patients with HF after acupuncture treatment. A dense vagal innervation of the auricle especially of the triangular fossa and concha has been suggested by Peuker et al. La Marca R et al found an increased vagal activity after electrical acupuncture on the concha of the ear. Electrical auricular vagal stimulation is a totally new approach to therapy in heart failure. It might be a safe complementary treatment in patients with chronic heart failure. As there are no clinical studies on this topic its effects on heart failure have to be further investigated.

## **5. OBJECTIVES OF THE CLINICAL INVESTIGATION (HYPOTHESIS)**

### **5.1 Primary Objectives (Hypothesis)**

In this study the effect of electrical auricular vagal stimulation on chronic heart failure will be assessed. Because of previous studies (Kristen et al.) we chose the following parameter as primary objective:

-6 min walk test

### **5.2 Secondary Objectives (Hypothesis)**

- Quality of Life assessed by SF 36
- adverse events of electrical auricular vagal stimulation will be recorded
- blood levels of inflammatory cytokines TNF  $\alpha$ , IL6, NT-proBNP, CRP
- LVEF (assessed by transthoracal echocardiography)
- NYHA (New York Heart Association) classification

## **6. DESIGN OF THE CLINICAL INVESTIGATION**

### **6.1 Population**

#### **6.1.1 Subject population**

40 patients with chronic heart failure aged from 18-85 will participate in this prospective, double-blind, randomised, placebo-controlled trial.

#### **6.1.2 Inclusion criteria**

- Chronic heart failure
- NYHA Classification II-III
- Stable medication since at least 1 months
- LVEF <40%
- Patients must be able to understand study conditions
- No exclusion criteria
- Signed informed consent

#### **6.1.3 Exclusion criteria**

- Any electrical auricular vagal stimulation treatment within 6 months prior to base line visit
- Participation in another clinical trial within 3 months prior to base line visit
- Ventricular tachyarrhythmia within 1 month prior to base line visit
- Psoriasis vulgaris
- Hemophilia
- Cardiac pace makers

#### **6.1.4 Duration of the clinical investigation**

Patients will stay in the study for 9 weeks consisting of 5 weeks treatment period and 4 weeks follow up period.

#### **6.1.5 Withdrawal and replacement of subjects**

##### **Criteria for withdrawal**

Subjects may prematurely discontinue from the clinical investigation at any time. Premature discontinuation from the study is to be understood when the subject did not undergo EOS

examination and / or all pivotal assessments during the clinical investigation, i.e. three complete dosage-time profiles.

Subjects must be withdrawn under the following circumstances:

- at their own request
- if the investigator feels it would not be in the best interest of the subject to continue
- if the subject violates conditions laid out in the consent form / information sheet or disregards instructions by the clinical investigation personal

In all cases, the reason why subjects are withdrawn must be recorded in detail in the CRF and in the subject's medical records. Should the clinical investigation be discontinued prematurely, all clinical investigation materials (complete, partially completed and empty CRFs) will be retained.

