#### **Follow-up of patients withdrawn from the clinical investigation**

In case of premature discontinuation after treatment with the medical device , the investigations scheduled for the EOS visit will be performed **7** days after discontinuation. The subjects will be advised that participation in these investigations is voluntary. Furthermore, they may request that from the time point of withdrawal no more data will be recorded and that all biological samples collected in the course of the clinical investigation will be destroyed.

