#### **Premature permanent discontinuation due to an adverse event**

If the reason for premature permanent discontinuation of clinical investigation is an AE, the patient should have a "Premature EOS" visit with all the assessments performed before the discontinuation of the treatment with the medical device, whenever possible.

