#### **Premature permanent discontinuation due to another reason than adverse event**

If the reason for premature permanent discontinuation of clinical investigation is not an AE, the patient should be withdrawn (withdrawal of consent) and have the EOS visit with all the assessments performed before the medical device discontinuation, whenever possible.

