#### **Intention to treat set**

This analysis set includes subjects who were randomized and received at least one dose medical device Main analysis is by the intention-to-treat principle. Here, an outcome value is necessary for each patient, if a patient drops out. Therefore, we will use the interim assessment of walking distance after 2 weeks of treatment, or, if this is unavailable, the baseline measurement (i.e., the patient is counted as a non-responder to treatment) as replacement in such cases.

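### The withdrawal rules take non-adherent patients and non-AE stoppers out of the study before the Day 63 walk, and the intention-to-treat analysis then imputes the walks lost this way

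*Combined protocol and SAP*

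**What the plan says.** **Who leaves.** Section 6.1.5 (Criteria for withdrawal) states "Subjects must be withdrawn under the following circumstances", and the last item on its list is "if the subject violates conditions laid out in the consent form / information sheet or disregards instructions by the clinical investigation personal". The heading and context concern leaving the investigation, not only stopping the device. The same section defines premature discontinuation partly by missing "three complete dosage-time profiles".

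**Non-AE stops.** Under 7.2.3, for discontinuation of the investigation for a reason other than an adverse event, "the patient should be withdrawn (withdrawal of consent) and have the EOS visit with all the assessments performed before the medical device discontinuation", where that can be done. The parallel paragraph for adverse events asks for a premature end-of-study visit at the same time point and does not mention consent.

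**What is measured afterwards.** Section 6.1.5 (Follow-up of patients withdrawn) sets the end-of-study investigations 7 days after discontinuation, and "The subjects will be advised that participation in these investigations is voluntary". A withdrawn patient may also ask that recording stop. Section 7.6.2 places the final walk at V5, Day 63, with one interim walk on Day 21.

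**What the analysis does.** Section 10.1 keeps everyone randomised and treated in the main set: "Here, an outcome value is necessary for each patient, if a patient drops out". The replacement is the two-week walk or, failing that, the baseline walk. Section 10.5 applies last observation carried forward to missing data generally.

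**The concern.** An intention-to-treat analysis needs outcomes on patients whether or not they adhere. Here the protocol itself ends participation for non-adherence, and it records a patient who stops for a non-AE reason as having withdrawn consent, even if that patient would have come back for a walk test. The outcome is then filled in at analysis. Revising the imputation rule cannot recover a walk that was never taken.

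Unequal withdrawal is plausible. The verum device delivers current through needles in the ear and the comparator is a dummy, so reasons for not following instructions may differ by arm. With 20 patients per arm, a few one-sided withdrawals move the primary estimate by several metres.

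**Working it through.** **1. The plan's own figure.** Difference 30 m, SD of improvement 30 m, two-sided 0.05, two-group t-test (section 10.2). The exact calculation gives n = 16.71, so 17 per group, with power 80.7%. Allowing 15% loss, 17 / 0.85 = 20. With all 20 per arm measured and the full effect, power is 86.9%. The sample size is sound.

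**2. The rules side by side.**

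| Point | One place | Another place |
|---|---|---|
| Time of early end-of-study assessments | 7 days after discontinuation, voluntary (6.1.5) | before device discontinuation, where possible (7.2.3, both paragraphs) |
| What is being stopped | the investigation (opening of the 7.2.3 paragraphs) | the device (timing of the visit in the same paragraphs) |
| Value used for a drop-out | two-week walk, else baseline (10.1) | last observation, which would include an early end-of-study walk (10.5) |
| Walk on Day 63 after leaving | not requested | V5 exists for everyone else (7.6.2) |

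The two timings conflict and must be reconciled. One patient can also receive two different primary values, depending on whether 10.1 or 10.5 is applied.

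**3. Bias from baseline substitution.** Let k1 and k0 be the numbers withdrawn (verum, placebo), and m1 and m0 the mean Day 63 changes those patients would have shown. Substituting baseline sets their change to 0. Relative to measuring them, the estimated difference therefore shifts by

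shift = −(k1·m1 − k0·m0) / 20.

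Assumptions not in the documents: both arms improve by 20 m, the device adds 30 m in those who continue, and no Day 21 value exists for those who leave.

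*5 verum, 1 placebo withdrawn*
- Substitution: (15×50)/20 − (19×20)/20 = 37.5 − 19 = 18.5 m.
- Measured, device effect lost: (15×50 + 5×20)/20 − 20 = 22.5 m. Shift −(5×20 − 20)/20 = −4 m.
- Measured, half the effect kept: (15×50 + 5×35)/20 − 20 = 26.25 m. Shift −(5×35 − 20)/20 = −7.75 m.

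*3 and 3 withdrawn*
- Substitution: 42.5 − 17 = 25.5 m.
- Measured, effect lost: 45.5 − 20 = 25.5 m. Shift 0.
- Measured, half kept: 47.75 − 20 = 27.75 m. Shift −2.25 m.

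*No true effect, 0 verum and 6 placebo withdrawn*
- Substitution: 20 − (14×20)/20 = +6 m. Measured: 0 m.

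**4. Power of the planned ANCOVA, by simulation.** 20 per arm. An assumed SD of 80 m at both times with a change SD of 30 m implies a correlation of 1 − 30²/(2×80²) = 0.93.

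| Scenario | Baseline substituted | Measured, effect lost | Measured, half kept |
|---|---|---|---|
| 5 v 1 | 18.6 m, 42% | 22.6 m, 62% | 26.4 m, 77% |
| 3 v 3 | 25.5 m, about 75% | 25.4 m, about 74% | 27.7 m |
| 0 v 6, no true effect | 6 m, type I error about 10% | 0 m, 5% | (no effect to keep) |

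The simulated means agree with the hand calculation to within 0.2 m. The powers move by one or two points between runs.

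**The case against.** **The plan does seek a walk after withdrawal.** A reader might infer that withdrawn patients are simply lost. They are not: 6.1.5 and 7.2.3 both call for the end-of-study assessments, and the walk is among them. This stands. But that walk is voluntary or conditional, is not taken on Day 63, and is not named as a replacement in 10.1.

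**Not every stopped device is a withdrawn consent.** The 7.2.3 paragraph opens with discontinuation of the investigation, and only its timing refers to the device. It is ambiguous rather than a plain rule that every non-AE device stop ends consent. A device that stings might also be recorded as an adverse event, in which case the consent label would not apply. This stands too, though the adverse-event paragraph likewise asks for no Day 63 walk.

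**The bias is not 11 m.** An ANCOVA on observed patients returns about 30 m and 80% power in the 5 v 1 case, so a reader might set 18.6 m against 30 m. That comparison assumes withdrawal is unrelated to outcome and that those who leave would have had the full effect. It is also not what measuring them on Day 63 would yield. The relevant gap is about 4 m if they lose the effect and about 8 m if they keep half.

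**The inputs are unfavourable by choice.** Section 10.1 uses the two-week walk first. If that walk carried half the improvement (assumption), the 5 v 1 case gives (15×50 + 5×25)/20 − (19×20 + 10)/20 = 24.25 m. This lies between the two measured results above (22.5 and 26.25 m), so the bias is under 2 m either way. If there is no common improvement and the effect is lost, the shift is nil. The documents give no withdrawal rate, no imbalance and no placebo improvement, and withdrawals at the patient's own request would remain after any change.

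**Conclusion.** The point holds. As written, the plan removes patients who could have been measured on Day 63, does not separate stopping the device from leaving the study, and imputes the missing walks. Two further contradictions come with it: the timing of the early end-of-study visit, and 10.1 against 10.5 on which value replaces a missing walk. The definition by dosage-time profiles matches nothing in the visit schedule.

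The size is conditional. For 5 v 1 withdrawn with baseline substituted, the avoidable loss is about 4 m and 20 points of power (62% against 42%) if stoppers lose the device effect, and about 8 m and 35 points (77% against 42%) if they keep half. For 3 v 3, the number implied by 20 against 17 per group, it is nil to about 2 m. One-sided placebo withdrawal can create a false benefit (6 m, type I error about 10% for 0 v 6), so the rule is not reliably conservative. All of this rests on an assumed common improvement of 20 m and, for power, a baseline SD of 80 m. It shrinks where a Day 21 walk exists. The material does not show that large or unequal withdrawal will occur, nor that the sample size is wrong. It shows an avoidable exposure that is cheap to close.

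**What to change.** Leave the rules for stopping the device as they are. Then:

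- In 6.1.5 and in both discontinuation paragraphs of 7.2.3, state that patients who stop the device or do not follow instructions remain in the study and are asked to attend V5 on Day 63, unless they withdraw consent to follow-up.
- Record withdrawal of consent only when the patient withdraws it.
- In the definition of premature discontinuation, replace the dosage-time profiles by the Day 63 6-minute walk.
- Reconcile the two timings of the early end-of-study visit (6.1.5 against 7.2.3), and state in 10.1 and 10.5 which single rule applies when an early walk exists but the Day 63 walk does not.

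The cost is protocol wording. V5 is already scheduled, so no visit is added. The downside is some effort to bring back a few patients. Those who refuse follow-up will still be missing.

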#### **Follow-up of patients withdrawn from the clinical investigation**

In case of premature discontinuation after treatment with the medical device , the investigations scheduled for the EOS visit will be performed **7** days after discontinuation. The subjects will be advised that participation in these investigations is voluntary. Furthermore, they may request that from the time point of withdrawal no more data will be recorded and that all biological samples collected in the course of the clinical investigation will be destroyed.

#### **6.1.6 Premature termination of the clinical investigation**

The sponsor has the right to close this clinical investigation at any time. The IEC and the competent regulatory authority must be informed.

The clinical investigation or single dose steps will be terminated prematurely in the following cases:

- If adverse event/adverse devise effect occur which are so serious that the risk-benefit ratio is not acceptable
- If the number of dropouts is so high that proper completion of the clinical investigation cannot realistically be expected.

## **7. METHODOLOGY**

After signing the informed consent patients will be randomized in the verum group (VA) or the placebo group (PA). Patients in the VA group will receive the P-STIM

